2.8 Baseline Assessment

We will ask participants to complete a questionnaire collecting detailed demographics, vehiclerelated risks, and impulsivity traits. This survey takes about 5 minutes to complete *See Appendix for Survey Questions*. We will also ask participants to complete the 5-Trial Adjusting Delay Discounting Task (Kaffaurnus & Bickel, 2014) to assess monetary impulsivity trait. All cohorts will complete identical baseline assessments.

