2.10 SMS Run-in

All participants will complete a 2-week run-in period where they complete weekly SMS assessments related to their target risk behavior without receiving any feedback or goal support. The primary purpose of the run-in is to exclude noncompliant subjects. Only participants who respond to at least 50% of the SMS queries in week 1 & 2 will be eligible to continue in the study. The secondary purpose is to identify the post-enrollment/ pre-intervention vehicle risk behaviors that may occur as a result of assessment reactivity. We expect that simply the act of enrolling in a study about vehicle risk and completing weekly SMS assessments of risk may result in reduced risk behaviors.

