2.11 Allocation to Treatment

Participants in each cohort who meet run-in criteria will be randomized in a 1:1 ratio to either the SMS intervention or SMS self-monitoring in blocks of 4. The randomization will be stratified according to site (i.e. ED). An independent statistician will create the randomization list using a random number generator. The randomization list will be stored in an electronic database to be unblinded once trial enrollment and follow-up periods have been completed.

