4. SAMPLE SIZE CALCULATION AND STATISTICAL ANALYSIS PLAN

4.1 Sample size calculation

The study has been powered to have at least 80% power for the primary outcome for Cohort 1 (seat belt use). Based on Sommers et al., 2013, we can likely expect the intervention to increase the percentage of subjects reporting seat belt use by15% on top of self-monioting alone. Using a 2-sample test of proportions, estimating 25% of the intervention participants and 10% of the control (SMS self-monitoring) report always seat beltuse, we would need around 100 subjects per group to show a significant difference between arms. Expecting 10% drop-out in the SMS 2-week run-in and 80% completing 8-week assessments, 300 enrolled in the ED should provide an analyzed sample of 216 (108 per arm).

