4.2.2 Primary Analysis

At baseline, all participants (based on screening criteria) all had the risk factor. At subsequent time points, participants are analyzed as having/not having the same risk factor by randomized group. For our primary analysis, we will examine the proportion of participants in each group (SMS intervention; assessment control) who report the risk behavior using a chi-squared test of proportions. We will then perform a logistical regression, entering any baseline attribute that has univariate association with the outcome in the final model. We will report the difference in percentage with primary outcomes as well as odds ratios (from logistical regressions) with 95% confidence intervals The α level is set at .05 for all statistical tests.

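### Free improvement: name the covariates of the logistic model in advance; as written, neither the ED stratification factor nor run-in risk is guaranteed to be in it

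*Combined protocol and SAP*

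**What the plan says.** Section 4.2.2 analyses the primary outcome in two steps. The first compares the arms "using a chi-squared test of proportions", which agrees with the sample-size method in section 4.1 ("Using a 2-sample test of proportions"). The second is a model: "We will then perform a logistical regression, entering any baseline attribute that has univariate association with the outcome in the final model". The reported odds ratios and their 95% intervals come from this second step.

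For the model there is no candidate list, no forced term and no entry threshold. The nearest thing to a threshold is the general statement that the alpha "level is set at .05 for all statistical tests". No other section names its covariates; the covariate rule for the GEE in section 4.2.3 is data-driven too.

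Four other statements bear on the point:
- Section 2.11, on allocation: "The randomization will be stratified according to site (i.e. ED").
- Section 2.10, on the run-in: "The secondary purpose is to identify the post-enrollment/ pre-intervention vehicle risk behaviors that may occur as a result of assessment reactivity".
- Section 2.8, on the questionnaire given before the run-in: "All cohorts will complete identical baseline assessments".
- Section 4.2.2, on the starting point: "At baseline, all participants (based on screening criteria) all had the risk factor".

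**The concern.** A rule that picks covariates by their association with the outcome cannot be resolved until week-8 outcomes are in. The content of the model behind a headline estimate is then unknown when the plan is signed.

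Two omissions matter in this trial. ED was used to stratify randomisation, but it enters only if it passes the screen. Run-in behaviour is the pre-randomisation measure closest to the outcome, and section 2.10 expects enrolment and weekly assessment alone to lower risk. It may not even be a candidate: section 4.2.2 ties baseline to screening, the baseline survey precedes the run-in, and section 4.2.3 lists baseline data and prior SMS reports separately. The yes/no screening risk cannot stand in for it, because every participant has it.

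At stake is whether the adjusted odds ratio has known content and respects the design. The primary test is not at stake.

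**Working it through.** **The plan's own figures reproduce.** Inputs from section 4.1: 25% v 10% always using a belt, 80% power, 10% run-in loss, 80% completing week 8. The two-sided .05 level is in section 4.2.1.
- Per group, pooled variance: [1.960 × √(2 × 0.175 × 0.825) + 0.842 × √(0.25 × 0.75 + 0.10 × 0.90)]² / 0.15² = 99.5, so 100.
- Analysed: 300 × 0.9 × 0.8 = 216, or 108 per arm. Power at 108 per arm is 83.1%.

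**Candidate items.** The appendices and section 2.8 give 13 screening items, 14 baseline items, 5 on driving and substance use, 1 delay-discounting score and 1 S-UPPS score: 34 in all. How many are unrelated to the outcome is unknown; 15 and 25 are used as assumptions.

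**Unrelated items entering.** With k independent unrelated items and a .05 screen (assumed), the expected number is 0.05k and the chance of at least one is 1 − 0.95^k.
- k = 15: 0.75 expected; 1 − 0.95^15 = 54%.
- k = 25: 1.25 expected; 1 − 0.95^25 = 72%.

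**ED and run-in risk.** These come from 2,000 simulated trials per setting: 108 per arm, 10% v 25%, four equal EDs (section 2.2 gives four) with arms balanced within ED, 15 unrelated items and a .05 screen. Run-in risk is binary with 30% prevalence. The strengths are assumptions, because the documents give none.

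| Between-ED SD (log-odds), run-in OR 5 | ED enters | ED left out |
|---|---|---|
| 0 | 4.7% | 95.3% |
| 0.3 | 19.5% | 80.5% |
| 0.5 | 49.9% | 50.1% |
| 0.8 | 89.0% | 11.0% |

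| Run-in OR, ED SD 0.3 | Run-in enters, if a candidate |
|---|---|
| 1 | 5.3% |
| 2 | 41.2% |
| 3 | 78.0% |
| 5 | 97.9% |
| 8 | 100.0% |

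**Type I error.** In three null settings the selected model gave 3.8% to 5.4% and the fixed model (treatment, ED, run-in) 3.8% to 5.6%, with a Monte Carlo SE of about 0.5 points. Selection causes no inflation.

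**Power of the logistic treatment test.** In the settings above, selected 83.0% to 89.4% and fixed 83.5% to 90.4%; setting by setting, fixed is ahead by 0.5 to 1.8 points. Those settings make every other candidate noise. With four further prognostic items at log-odds 0.6 per SD (n = 216, 25 candidates, 1,500 replicates), the order reverses: fixed 85.8%, selected 87.9%.

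**Model size.** Expected always-users: 108 × 0.25 + 108 × 0.10 = 37.8. Treatment (1), ED (3) and run-in (1, or 2 with a third level) make 5 or 6 terms: 37.8/5 = 7.6 or 37.8/6 = 6.3 always-users per term. The list has to stay short.

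**The case against.** The strongest reply is that little depends on this model. The chi-squared test is labelled primary, is valid without ED, and delivers the stated power. The effect on the estimate is also modest. In simulations under assumed strengths, the selected odds ratio differed from the fixed one by a median factor of 1.04 to 1.09. The sampling interval is far wider: at 27/108 v 10.8/108, SE(log OR) = √(1/27 + 1/81 + 1/10.8 + 1/97.2) = 0.39, a factor of exp(1.96 × 0.39) = 2.15 each way. Part of any shift is non-collapsibility, not error. All of this stands, and it limits the size of the point.

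A second reply is that a screen favours real predictors. This also stands. A reader might infer that ED and run-in risk get in only by luck, but the tables do not support that: a strong run-in predictor nearly always passes if it is a candidate. The accurate statement is that entry is not guaranteed and is settled by the outcome data.

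Third, a short fixed list omits norms, control, perceived danger and impulsivity, which sections 1.3, 4.2.3 and 4.2.4 treat as relevant. If these are strongly prognostic, selection can have slightly more power. A reader might infer that naming covariates buys power over selection; the direction is unknown, so that is not claimed.

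A reader might also infer that the rule lets the team choose covariates to suit the result. Section 4.2.1 blinds the analysts and labels the groups A and B until the pre-specified analyses are done, and the screen looks at the outcome, not at the treatment effect. The documents do not support that reading.

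Finally, excluding run-in behaviour from the baseline attributes is an inference; section 4.2.2 does not define the term. That ambiguity is itself a reason to settle it in writing.

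**Conclusion.** The point holds as a free improvement of minor to moderate size. The model that yields the reported odds ratios has no pre-specified content. It may omit the stratification factor and the closest pre-randomisation measure of the outcome, and it may admit unrelated items. The benefit of fixing the covariates is an adjusted odds ratio that is settled before outcomes are seen and that respects the stratified randomisation. The chi-squared result, the percentage difference, the planned power and the type I error are untouched.

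The frequencies rest on assumptions: a .05 screen, 15 or 25 unrelated and independent items, the between-ED spread and the strength of run-in risk. The ED figure in particular runs from about 11% to 95% left out, and no single value should be quoted as the expected one. The absence of a named list and of forced terms needs no assumption; it is in the text.

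**What to change.** In section 4.2.2, delete selection by univariate association and write in the following:
- **Covariates, all cohorts:** treatment, ED and run-in target risk. Add no others to the main adjusted model, given 5 to 6 terms for about 38 expected always-users in Cohort 1.
- **Sparse EDs:** in any cohort, including Cohort 1, collapse EDs to city (the Pittsburgh and Philadelphia sites of the synopsis) if an ED has randomised fewer than 10 participants. Cohort 1 needs this too, because section 8.2 makes enrolment competitive without caps and section 2.2 allows added sites.
- **Run-in risk:** any target risk reported in the answered run-in weeks, coded yes or no, with no trip or no usable report as its own level. If that level is sparse, merge it by a rule fixed now and blind to outcome and arm. Do not count unusable reports as no risk by default, since section 4.2.3 handles missing outcomes by worst performance.
- **Status:** one sentence saying that chi-squared is the deciding test and the adjusted odds ratio is supportive. Outcome-driven selection, if kept, is a labelled sensitivity analysis.

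The cost is a few lines of text and a simple derivation from SMS data already collected. The three-level run-in coding was not simulated, so its behaviour should be checked on simulated or blinded data before the SAP is final.

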4.2.3 Secondary Analyses

The percentage of ED patients who screen positive and agree to enroll, the percentage of ED patients who enroll who meet run-in criteria, the percentage of ED patients enrolled in the Intervention arm who complete at least 50% of the SMS assessments during the intervention period, and the percentage of ED patients enrolled in the Intervention arm who found the program helpful will be calculated and presented with 95% confidence intervals. We will explore whether individual factors (e.g. sex, race, education) are associated with enrolling, meeting run-in criteria, completing SMS assessments or finding the program helpful using multi-level modeling. We will examine whether perceived norms, perceived control, or perceived risk differed between treatment arms. We will explore the slope of change over time in SMS risk reports using generized estimating equations (GEE) with log link function, examining time, treatment and time*treatment effects. Any individual factors signifianctly associated with SMS assessment completion will be included as

covariates.GEE is the recommended technique to handle non-parametric residuals and missingness associated with repeated-measured data. We will use robust estimates and account for clustering of outcome data within individuals. Results will be presented as odds ratios with 95% confidence intervals.

Handling Missing Outcome Data: If a participant is missing outcome assessment time points (week 8 or week 14), vehicle risk behavior will be imputed based on a pre-defined plan as follows. If a participant has reported that risk via SMS weekly reports, we will use those values for missing weeks. If either of the prior 2 weeks is missing on both web-based recall report or SMS reports, we will impute the missing week based on the worst performance recorded in the weeks either before or after the missing one using SMS values. We believe that this will provide the most conservative estimate of the missing value. Sensitivity analyses will be performed using various other imputation techniques, including multiple chained imputations using baseleine and prior SMS reports.

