4.2.4 Subgroup analyses

The analysis will include three pre-defined subgroup analyses for the primary and key secondary outcomes according to 1) participants with high baseline impulsivity (based on delay discount task or self-report (S-UPPS); 2) participants with low perceived danger (defined as those who report No danger associated with target vehicle risk); and 3) participants with low perceived control (i.e. disagree with being able to control behavior). These cut-off were chosen to represent a population with the highest predicted likelihood of injury due to vehicle risks. The trial is not powered to detect subgroup differences and these will be considered exploratory and hypothesis generating.

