Appendix: Baseline Questions

Quest ion Who do you live with?	l live alone	Friend(s), same sex	Friend(s), other sex	Parents or family		
Code livew	0	1	2	3		
Quest ion	No	Yes, part- time	Yes, full time			
Code emply	0	1	2			
Quest ion	Uncomfortab le	Forgot	Don't think they help	Like freedo m	Other	l always wear my seat belt
Code seatbelt_reasons	0	1	2	3	4	5
Quest ion If other, state reasons						
Code seatbelt_other						
Quest ion	Never	Rarely	Most of the time	Always		
Code	0	1	2	3		
Quest ion How dangerous is it to not wear a seat belt?	Not at all	Somewhat	Very	Comple tely		
Code danger_seatbelt	0	1	2	3		
Quest How much do you agree: I have complete control over whether I wear a ion seat belt.	Strongly Disagree	Disagree	Somew hat Agree	Mostly agree	Strongly Agree	
Code control_sb	0	1	2	3	4	
Quest Check off all the reasons you have typed on your phone while driving? ion	l could not wait	I don't think it affects my driving	It was an emerge ncy	lt is fun	l get bored driving	l do not use my phone while driving
Code twd_reasons	0	1	2	3	4	5
Quest ion How often do your friends type on their phones while driving?	Never	Rarely	Most of the time	Always		
Code	0	1	2	3		
Quest ion How dangerous is it to type on your phone while driving?	Not at all	Somewhat	Very	Comple tely		
Code danger_twd	0	1	2	3		
Quest How much do you agree: I have complete control over whether I type on ion my phone while driving.	Strongly Disagree	Disagree	Somew hat Agree	Mostly agree	Strongly Agree	
Code control_twd	0	1	2	3	4	
Quest Check off all the reasons you have driven a car after drinking alcohol? ion	l had no other opiton	I don't think it affects my driving		l am careful	It is fun	l do not drive after dirnking alcohol
Code dd_reasons	0	1	2	3	4	5
Quest ion How often do your friends drive after drinking alcohol?	Never	Rarely	Most of the time	Always		
Code friends_dd	0	1	2	3		
Quest How dangerous is it to drive soon after drinking more 3 or more alcoholic ion drinks?	Not at all	Somewhat	Very	Comple tely		
Code danger_dd	0	1	2	3		

Quest How much do you agree: I have complete control over whether I type on ion my phone while driving.	Strongly Disagree	Disagree	Somew hat Agree	Mostly agree	Strongly Agree
Code control_dd	0	1	2	3	4

Quest Answer the following questions about yourself.	Strongly Disagree	Disagree	Somew hat Agree	Mostly agree	Strongly Agree	
cat code	0	1	2	3	4	
Questi When I feel bad, I will often do things I later regret in order to make myself on feel better now.						

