Appendix: 8-Week Assessment

	been in a car over the past 2 weeks.				
Questi on	How often have you driven a car?	Never	A few times	Most days	Every day
Code	driver	0	1	2	3
Questi on	How often did you wear a seat belt when you drove a car?	Never	A few times	Most of the time	Always
Code	drive_seatbelt	0	1	2	3
Questi on	How often have you been a passenger in the front seat of a car?	Never	A few times	Most days	Every day
Code	pass_front	0	1	2	3
Questi on	How often did you wear a seat belt when you were a passenger in the front seat ?	Never	A few times	Most of the time	Always
Code	pass_seatbelt1	0	1	2	3
Questi on	How often have you been a passenger in the back seat of a car?	Never	A few times	Most days	Every day
Code	pass_back	0	1	2	3
Questi on	How often did you wear a seat belt when you were a passenger in the back seat?	Never	A few times	Most of the time	Always
Code	pass_seatbelt2	0	1	2	3
Questi on	How often did you type on your phone while you were driving and when the car was moving?	Never	A few times	Most of the time	Always
Code	distract	0	1	2	3
Questi on	What's the most number of alcoholic drinks you've had prior to driving on any occasion?	#			
Code	drinks	#			

The following questions ask you to recall times you have been in a car over the past 2 weeks.

Questi on	Check off all the reasons you have not used a seat belt	Uncomfort able	Forgot	Don't think they help	Like freedom	Other	l alway s wear my seat belt	
Code	seatbelt reasons	0	1	2	3	4	5	
Questi on	lf other, state reasons							
Code	seatbelt_other							
Questi on	How often do your friends use their seat belt?	Never	Rarely	Most of the time	Always			
Code		0	1	2	3			
Questi on	How dangerous is it to not wear a seat belt?	Not at all	Somew hat	Very	Comple tely			
Code	danger_seatbelt	0	1	2	3			
Questi on	How much do you agree: I have complete control over whether I wear a seat belt.	Strongly Disagree	Disagre e	Somew hat Agree	Mostly agree	Stron gly Agree		
Code	control_sb	0	1	2	3	4		
Questi on	Check off all the reasons you have typed on your phone while driving?	l could not wait	l don't think it affects my driving	It was an emerge ncy	It is fun	l get bored drivin g	l do not use my phon e while drivin g	l do not dri ve
Code	twd reasons	0	1	2	3	4	9 5	6
Questi on	How often do your friends type on their phones while driving?	Never	Rarely	Most of the time	Always			
Code		0	1	2	3			

SaVE Trial Protocol v.1.0 Page **33** of **36**

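### The arm comparison of perceived norms, control and risk does not specify adjustment for the same items at baseline, so it permits a less precise analysis than the collected data allow

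*Combined protocol and SAP*

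**What the plan says.** Section 4.2.3 gives this analysis one sentence: "We will examine whether perceived norms, perceived control, or perceived risk differed between treatment arms". It does not name the items, the assessment week, the scale, the model or any covariate.

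The Appendix of baseline questions has a danger item (for seat belts, "How dangerous is it to not wear a seat belt", coded 0–3), a control item (coded 0–4) and a friends item (for typing, "How often do your friends type on their phones while driving", coded 0–3). The 8-week and 14-week appendices repeat them with the same response levels, for example "How much do you agree: I have complete control over whether I wear a seat belt" at week 8. The stem of the baseline seat-belt friends item is not legible in the text I had, but its response row is there.

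Section 2.8 says "All cohorts will complete identical baseline assessments". That survey comes before the run-in (2.10) and randomisation (2.11).

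The plan has two covariate rules. Section 4.2.2 speaks of "entering any baseline attribute that has univariate association with the outcome in the final model", for the risk-behaviour outcome. Section 4.2.3 adds factors related to SMS completion, for the GEE of SMS risk reports. Section 4.2.4 uses perceived danger and perceived control only to define subgroups.

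**The concern.** Section 1.6 says the messages aim to change the cognitive and motivational factors of the two behavioural theories. The sentence in 4.2.3 is the only planned between-arm comparison of those perceptions. It rests on single items with four or five levels, in a trial powered only for the Cohort 1 behaviour outcome.

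If a person's answer at week 8 resembles that person's answer at baseline, a comparison of follow-up answers alone leaves predictable variation in the error term. The data to remove it are already planned, and they are valid covariates because they precede randomisation. At stake is the width of the confidence interval for the mechanism result, most of all in the small Cohorts 2 and 3. Silence also leaves model, week and covariates to be chosen once the data are in hand.

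**Working it through.** **1. The plan's own figures.** Section 4.1 assumes 25% against 10%, with 80% power; 4.2.1 sets two-sided 0.05. With pooled variance under the null and no continuity correction:

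n = [1.960·√(2·0.175·0.825) + 0.842·√(0.25·0.75 + 0.10·0.90)]² / 0.15² = 99.5, so 100 per group, as stated.

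Analysed sample: 300 × 0.9 × 0.8 = 216, or 108 per arm, as stated. No figure is given for the perception comparison.

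**2. Does any stated rule supply the adjustment?** The screening rule in 4.2.2 concerns the primary outcome, the completion covariates belong to the GEE, and 4.2.4 forms subgroups. None reaches this comparison, and none excludes baseline adjustment.

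**3. Size of the gain for a mean difference.** The input r, the correlation of the same item at baseline and follow-up on the observed scale, is not in the documents, so a range is assumed. Against the unadjusted follow-up comparison:

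- variance ratio = 1 − r²; standard-error ratio = √(1 − r²)
- equivalent n per arm = 108 / (1 − r²)
- detectable difference at 80% power = (1.960 + 0.842)·√(2(1 − r²)/n), in SD units

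| r (assumed) | Variance cut | SE ratio | Equivalent n per arm | Detectable, n = 108 | Power for an assumed 0.3 SD, n = 108 | Detectable, n = 36 |
|---|---|---|---|---|---|---|
| 0 | 0% | 1.000 | 108 | 0.381 | 60% | 0.660 |
| 0.1 | 1% | 0.995 | 109 | 0.379 | 60% | 0.657 |
| 0.3 | 9% | 0.954 | 119 | 0.364 | 64% | 0.630 |
| 0.5 | 25% | 0.866 | 144 | 0.330 | 72% | 0.572 |
| 0.7 | 49% | 0.714 | 212 | 0.272 | 87% | 0.472 |

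The n = 36 column assumes Cohort 1 retention in Cohorts 2 and 3: 100 × 0.9 × 0.8 = 72. Section 4.1 gives retention only for Cohort 1.

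**4. Coarse items.** Linear models were simulated on a four-level item at 108 per arm, 6,000 runs per setting, with an assumed latent correlation of 0.5. When the levels held 10/30/35/25% of answers, the observed r was 0.44 and the SE ratio 0.897 (variance cut 1 − 0.897² = 20%). With a ceiling (3/12/25/60%), the observed r was 0.40 and the SE ratio 0.917 (cut 1 − 0.917² = 16%). The formula in step 3 predicts these ratios when the observed r is used.

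**5. Proportional-odds model.** Here the gain takes another form. With an assumed latent shift of 0.3 SD at 108 per arm, the median standard error of the log odds ratio rose slightly, from 0.250 to 0.253, 0.258 and 0.270 at latent correlations of 0.3, 0.5 and 0.7. Power rose from 52% to 56%, 57% to 65% and 51% to 77%. The runs were few (300, 150 and 150), so each power figure carries a Monte Carlo error of about 3 to 4 points (for example √(0.57·0.43/150) = 0.04). The three unadjusted figures differ for that reason. A second simulation (assumed shift 0.4 SD, evenly used levels, 300 runs per setting) gave about 78% unadjusted and 82%, 88% and 92% adjusted.

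**6. Cost of adjusting.** One degree of freedom for the baseline item multiplies the standard error by √(1 + 1/(2n − 4)): 1.002 at 108 per arm and 1.007 at 36. Section 2.2 names four EDs, so ED adds three terms.

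**7. One item does not measure its target.** In the baseline, 8-week and 14-week appendices, the item coded control_dd carries the same stem as control_twd: control over typing on the phone while driving. Adjusting it for its own baseline cannot make it a measure of control over drink driving.

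**The case against.** A reader might infer that the plan has chosen to ignore the baseline answers and compare raw follow-up values. The documents do not support that. The sentence names no method, so it neither plans nor rules out adjustment; the defect is an unspecified analysis that permits the weaker option.

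A reader might also infer that the unadjusted result would be misleading. Under randomisation it is unbiased, and chance baseline imbalance is the same precision issue seen from another side, not a second fault. Perceptions are not among the outcomes listed in 3.1, and 2.1 makes everything beyond the Cohort 1 primary outcome exploratory.

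The size is open to challenge too. No passage shows that people differ strongly and stably on these items. To say that the 216 would act like 216/0.75 = 288 needs an observed r of 0.5 and a mean difference as the estimand. It does not carry over to an odds ratio, whose interval adjustment does not narrow. Nor is adjustment wholly free: there are a few extra terms, and they weigh slightly more at about 36 per arm.

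All of this stands as a limit on the point. It does not remove it: the items are collected, nothing in the plan uses them here, and adjustment helps whenever r is appreciably above zero.

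**Conclusion.** The point holds as a gap in specification that permits an avoidable loss of precision in an exploratory analysis. It does not concern bias and leaves the primary result unchanged. The size depends on r, which the documents do not give: a variance cut of about 9%, 25% or 49% at assumed observed values of 0.3, 0.5 or 0.7, and next to nothing below about 0.2. Coarse or ceiling-heavy items sit lower in that range. The figures for Cohorts 2 and 3 also assume Cohort 1 retention. Perceived control in Cohort 3 is an exception that adjustment cannot repair while the item asks about typing.

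**What to change.** Replace the sentence in 4.2.3 with:

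> For the cohort's target behaviour, each perception item at week 8 (and, separately, week 14) will be compared between arms by a linear model with robust standard errors on arm, the same item at baseline and ED, reporting the adjusted mean difference with 95% CI; a proportional-odds model with the same covariates will be a sensitivity analysis.

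ED is included because 2.11 stratifies the randomisation by it. The linear model comes first so that the gain appears as a narrower interval for a quantity that keeps its meaning with or without the covariate.

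Add that perceived control in Cohort 3 is excluded from this analysis unless the control_dd stem is corrected at all three assessments. Where answers have already been collected with the present stem, they should not be reported as control over drink driving.

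The model change needs no new data. It costs one SAP sentence, one degree of freedom and the ED terms.

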Appendix: SMS Interventions: Seat belt Safety

Day & Time	Incomin	Outroing
Day & Time Qualified Week 3,	g	Outgoing
Monday, 5pm		
Qualified		Congratulations [Name]! You have qualified to continue the SaVE Study For the next 6 weeks, we will help you set goals and provide you personalized feedback on your seat belt use We will check in next Sunday. Until then, take care
Week 3-8: Sunday, 3pm		
2 hours 2 hours	[Missing] x1 [Missing] x2 [Nonsen se]	Hi [_NAME_], it's the SaVE Study Team checking in How often have you been a passenger or driver in a car the past week? 0=never; 1=a few times; 2=most days; 3=every day We missed your response. Text us how often you have been a passenger or driver in a car the past week? You must be busy. We will check in next week We don't understand. Please text us a response option: 0=never; 1=a few times; 2=most days; 3=every day
1 hour	0 1,2,3 [Missing] x1	OK When in the car, how often did you wear a seat belt? 0=never; 1=a few times; 2=most of the time; 3=every time We missed your response. Text us how often you wore a seat belt
1 hour	[Missing] x2 [Nonsen se]	You must be busy. We will check in next week We don't understand. Please text us a response option: 0=never; 1=a few times; 2=most of the time; 3=every time
If Goal Not Set	3	[Posiitve Reinforcement Message]
	0,1,2	[Social Norms Message]
If Goal Set	Goal met Goal not met	[Goal Met Message] [Goal Not Met Message]
		Would you be willing to commit to a goal to wear a seat belt every time this week?
1 hour	[Missing] x1 [Missing]	We missed your response. Text us whether you'd be willing to set a goal?
1 hour	x2 [Nonsen se]	You must be busy. We will check in next week We don't understand. Please text us either yes or no
No Goal	No	[No Goal Roll Library Message]
Goal +	Yes	[Goal Reinforcement Message]
Random 2 days per week, 4pm		
lf goal -		[Seat belt Safety Info Message]
lf goal +		[Goal Reminder Message]

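### Section 4.2.3 pairs a log-link GEE with odds ratios and wrongly relies on GEE itself to deal with missing weekly reports; the first is a plain contradiction, the second a gap of assumption-dependent size

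*Combined protocol and SAP*

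**What the plan says.** Section 3.1.4 lists slopes of change over time among the secondary effectiveness outcomes. Section 4.2.3 gives the method: "We will explore the slope of change over time in SMS risk reports using generized estimating equations (GEE) with log link function", with terms for time, treatment and their interaction, robust estimates, and clustering within individuals. The effect measure follows in the same paragraph: "Results will be presented as odds ratios with 95% confidence intervals".

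On missing weekly reports, the section says "GEE is the recommended technique to handle non-parametric residuals and missingness associated with repeated-measured data". It adds one further provision: "Any individual factors signifianctly associated with SMS assessment completion will be included as" covariates. The examples given earlier in the section are sex, race and education ("We will explore whether individual factors (e.g. sex, race, education) are associated with enrolling, meeting run-in criteria, completing SMS assessments").

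The imputation rules come under a separate heading and have a narrower scope: "If a participant is missing outcome assessment time points (week 8 or week 14), vehicle risk behavior will be imputed". The chained-imputation sensitivity analysis belongs to those same rules. For the weekly series the plan states no missingness assumption, no response weights and no working correlation.

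**The concern.** There are two separate problems in one paragraph.

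The first is internal. For a binary outcome, exponentiated coefficients from a log link are ratios of risks; odds ratios need a logit link. An analyst following the text must break one of the two instructions, or print risk ratios under the wrong name.

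The second is the statement about missingness. Unweighted GEE is generally consistent only when response is unrelated to the outcomes given the covariates in the model. Robust standard errors repair the variance, not this bias. Demographic covariates can absorb non-response that they drive, but not non-response driven by what a participant reported the week before.

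The design gives a reason to ask whether that happens differently by arm. Intervention participants get replies that depend on their report, including a "Goal Not Met Message" (Appendix: SMS Interventions: Seat belt Safety), while controls get none (section 2.13). If risk reports change later response in one arm only, the arm-by-time term can move away from its null value without any treatment effect.

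**Working it through.** **1. Link against effect measure.** Section 4.1 assumes that 25% (intervention) and 10% (control) always use a seat belt. The risks are therefore 1 − 0.25 = 0.75 and 1 − 0.10 = 0.90.

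- Risk ratio: 0.75 / 0.90 = 0.83.
- Odds ratio: (0.75/0.25) / (0.90/0.10) = 3 / 9 = 0.33.
- If the risk ratio were printed as an odds ratio, a reader starting from control odds of 9 would compute 9 × 0.8333 = 7.5, a risk of 7.5/8.5 = 88%, instead of 75%.

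These are week-8 levels used for illustration. The interaction term is a ratio of changes, but the same distinction applies to it.

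**2. Size of the missing-data problem.** The plan gives no figure for the slope analysis. Its inputs reproduce: 300 × 0.90 = 270 randomised, 135 per arm; 270 × 0.80 = 216 analysed, as section 4.1 states. Everything else is an assumption: no treatment effect, flat weekly risk of 70%, random intercept with SD 2, permanent dropout depending on the last report, weeks 3–8, the modified intention-to-treat filter of section 4.2.1, logit link, robust standard errors and 1,000 trials per row.

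Rejection rate of the arm-by-time test at 0.05:

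| Dropout pattern | Responding at week 8 | Independence | AR(1) | Exchangeable | Weighted |
|---|---|---|---|---|---|
| Unrelated to reports | about 83% | 4.7% | 4.6% | 3.8% | 4.1% |
| Report-dependent, same in both arms | about 83% | 4.1% | 4.6% | 3.9% | 4.0% |
| Report-dependent, intervention only | about 83% | 5.9% | 6.0% | 5.0% | 4.4% |
| Opposite direction by arm | about 82% | 8.9% | 7.2% | 5.8% | 5.2% |
| Intervention only, heavy | about 61% | 13.6% | 8.7% | 4.1% | 3.7% |
| Opposite, heavy | 60–63% | 39.2% | 22.0% | 5.8% | 4.9% |

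The simulation error around 5% is √(0.05 × 0.95 / 1000) = 0.69 points, so results between about 3.6% and 6.4% cannot be told apart from nominal. A log link with independence gave similar rates (up to 38.8%).

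The large-sample null odds ratios over weeks 3–8 with independence in the last four rows are 0.93, 0.85, 0.77 and 0.57 (true value 1). Weighting by inverse probability of response given arm and last report gives 0.98–1.02. Weekly risks of 50% and 85% show the same pattern. Exchangeable correlation is near 1 only when the true correlation is exchangeable; with serially correlated reports it gives 1.06 to 1.26, the opposite direction.

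**3. Other response patterns.** Here the differential acts in the intervention arm only, with the log-odds of non-response 0.7 or 1.0 higher after a risk report.

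- Permanent dropout over all 12 weeks: odds ratios 0.81 and 0.68, rejection 11% and 22%, with only 34–42% of intervention participants still responding.
- Six active weeks only, or intermittent gaps: odds ratios 0.91–1.08, rejection 4–6%.
- A further setting with intermittent gaps over 12 weeks and the differential ending at week 8: odds ratios 1.08 and 1.10, rejection 6% and 8%.

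**The case against.** The strongest case against is that the design limits the bias. Feedback stops after six weeks (section 2.12), so a feedback-driven difference between arms need not last through week 14. A non-responder is queried again the following week (SMS appendices), so gaps may be intermittent, and recurrent gaps shift the level more than the slope. The run-in removes poor responders (section 2.10). Section 3.1.4 defines slopes by period, not one slope over 12 weeks. Section 4.2.3 speaks of exploring the slope, and section 2.1 calls other outcomes exploratory. All of this stands and limits the size.

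It does not remove the point. The 80% in section 4.1 is completion of the week-8 web assessment, not weekly text response. Section 2.15 describes no payment for weekly texts after run-in, and the acceptability benchmark in section 3.1.3 is only half of the SMS assessments. Heavy weekly non-response is therefore not excluded.

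On the link, it may be said that log is a slip for logit, or that the odds-ratio sentence belongs to the multi-level models earlier in the paragraph. The first is likely enough and needs only a correction. The second would leave the GEE with no stated effect measure.

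A reader might infer that the slope analysis will make an ineffective intervention look effective. The documents do not support that. They give no data on response by arm and prior report, and the direction changes with the working correlation and the pattern of gaps.

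**Conclusion.** Two statements are wrong as written and need no assumptions to show it: a log link does not yield odds ratios, and unweighted GEE does not in itself handle missingness that depends on earlier reports. Nothing else in section 4.2.3 fills that gap for the weekly series.

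The consequence for the arm-by-time test is conditional. It requires report-dependent non-response that differs by arm; with the same mechanism in both arms the error stayed near 5%. Under the assumed mechanisms the false-positive rate is about 4–9% near 80% response or with intermittent gaps, and exceeds about 10% only with heavy permanent dropout. Response rates, strength of dependence, weekly risk and correlation are all assumed.

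A secondary, exploratory outcome is affected. The primary week-8 chi-squared test is not.

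**What to change.** In section 4.2.3:

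- Use a logit link and report odds ratios, or keep the log link and report risk ratios.
- Delete the claim that GEE handles missingness, and state the missingness assumption and the working correlation for the weekly series.
- Fit the slope GEE to weekly reports multiply imputed from baseline data, arm and earlier SMS reports, which extends the chained method already named for weeks 8 and 14. Alternatively, weight each observed week by the inverse probability of response given arm and earlier reports.
- Show the unweighted fit alongside.

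The link correction is free. The rest costs some wording, modest programming and possibly slightly wider intervals, which have not been quantified. As specified, neither remedy covers non-response that depends on the unreported behaviour of the missing week itself; the stated assumption should say so.
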